7.2.5 Behavior Rating Inventory of Executive Function–Adult Version (BRIEF-A)

The BRIEF-A is a standardized measure designed to assess adult executive functioning and self-regulation. It is composed of 75 items and 9 clinical scales which include: Inhibit, Self-Monitor, Plan/Organize, Shift, Initiate, Task Monitor, Emotional Control, Working Memory, and Organization of Materials. The clinical scales compose two indexes: Behavioral Regulation Index (BRI) and Metacognition (MI), and these indexes form the overall summary score, the Global Executive Composite (GEC). The BRIEF-A will be completed at Baseline (Visit 2) and Visit 7.

The BRIEF-A subscales, indices and overall summary score are scored as follows:

- BRIEF-A Inhibit subscale score (sum of items 5,16, 29, 36, 43, 55, 58, 73)
- BRIEF-A Self-Monitor subscale score (sum of items 13, 23, 37, 50, 64, 70)
- BRIEF-A Plan/Organize subscale score (sum of items 9, 15, 21, 34, 39, 47, 54, 63, 66, 71)
- BRIEF-A Shift subscale score (sum of items 8, 22, 32, 44, 61, 67)
- BRIEF-A Initiate subscale score (sum of items 6, 14, 20, 25, 45, 49, 53 62)
- BRIEF-A Task Monitor subscale score (sum of items 2, 18, 24, 41, 52, 75)
- BRIEF-A Emotional Control subscale score (sum of items 1, 12, 19, 28, 33, 42, 51, 57, 69, 72)
- BRIEF-A Working Memory subscale score (sum of items 4, 11, 17, 26, 35, 46, 56, 68)
- BRIEF-A Organization of Materials Subscale Score (sum of items 3, 7, 30, 31, 40, 60, 65, 74)
- BRIEF-A Behavioral Regulation Index (BRI) (sum of Inhibit, Shift, Emotional Control, Self-Monitor subscale scores)
- BRIEF-A Metacognition Index (MI) (sum of Initiate, Working Memory, Plan/Organize, Task Monitor, Organization of Materials subscale scores)
- BRIEF-A Global Executive Composite (GEC) Score (sum of BRI and MI scores)

7.2.6 Difficulties in Emotional Regulation Scale (DERS)

The DERS is a validated non-disease state scale consisting of 36 items scored on a range of 1 (almost never) to 5 (almost always). These items are grouped to reflect difficulties in: a) awareness and understanding of emotions; b) acceptance of emotions; c) ability to engage in goal directed behavior and refrain from impulsive behavior while experiencing negative emotions; and d) access to emotional regulation strategies perceived as effective. The DERS will be completed at Baseline (Visit 2) and Visit 7.

The following DERS scores will be assessed:

- DERS Non-acceptance subscale score (sum of items 11, 12, 21, 23, 25, 29)
- DERS Goals subscale score (sum of items 13, 18, 20R, 26, 33)
- DERS Impulse subscale score (sum of items 3, 14, 19, 24R, 27, 32)
- DERS Awareness subscale score (sum of items 2R, 6R, 8R, 10R, 17R, 34R)
- DERS Strategies subscale score (sum of items 15, 16, 22R, 28, 30, 31, 35, 36)
- DERS Clarity subscale score (sum of items 1R, 4, 5, 7R, 9)
- DERS total score (sum of all subscale scores)

Note: "R" indicates a reverse-scored item which is calculated by subtracting the item score rather than adding.

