### **6.3.6 Difficulties in Emotional Regulation Scale (DERS)**

The DERS is a validated non-disease state scale consisting of 39 items. These items are grouped to reflect difficulties in: a) awareness and understanding of emotions; b) acceptance of emotions; c) ability to engage in goal directed behavior and refrain from impulsive behavior while experiencing negative emotions; and d) access to emotional regulation strategies perceived as effective.

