## **9.5 Secondary Efficacy Analyses**

The primary analysis will be repeated on the PP population using the MMRM analysis described in Section [9.4](#).

The secondary efficacy outcomes include:

- AISRS hyperactivity/impulsivity subscale scores
- CGI-S
- CGI-I
- BRIEF-A

For the AISRS, the proportion of responders (defined as a subject who has a change from Baseline of 30% or greater in the AISRS) will also be presented.

The number and percentage of subjects who have each category of the CGI-S and CGI-I at each time point will be presented by treatment group. Cochran-Mantel-Haenszel row mean score tests will be used to compare the treatment groups. CGI-S and CGI-I results will also be summarized treating the responses as continuous values. A MMRM will be utilized to

compare treatments at each time point. The model will include fixed effects for treatment, week, and the treatment-by-week interaction.

BRIEF-A will be summarized descriptively over time utilizing observed and change from Baseline scores. Treatments will be compared at each time point utilizing MMRM models on change from Baseline scores. The model will include fixed effects for treatment, week, baseline value, and the treatment-by-week interaction.

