7. EFFICACY EVALUATION

7.1 Overview of Efficacy Analysis Issues

7.1.1 Handling of Dropouts or Missing Data

Missing data could occur under either or both of the following scenarios: (1) missing or invalid data for individual questions in the AISRS; and (2) missing AISRS total scores at individual visits. The approach to handling missing data under these scenarios is described below.

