7.4.2 Secondary Efficacy Analyses

The primary analysis will be repeated on the FAS population using the mixed model repeated measures analysis described in Section 7.4.1.

The secondary efficacy outcomes include:

- Changes from Baseline of AISRS hyperactivity/impulsivity and inattentive subscale scores compared to Visit 7
- CGI-S at Visit 7 compared to Baseline
- CGI-I at Visit 7
- Changes from Baseline of the BRIEF-A, subscales, indices, and composites compared to Visit 7

For the AISRS, the proportion of responders (defined as a subject who has a change from Baseline of 30% or greater in the AISRS) will also be presented.

The number and percentage of subjects who have each category of the CGI-S and CGI-I at each time point will be presented by treatment group. Cochran-Mantel-Haenszel row mean score tests will be used to compare the treatment groups. CGI-S and CGI-I results will also be summarized treating the responses as continuous values. A MMRM will be utilized to compare treatments at each time point. The model will include fixed effects for treatment, week, and the

treatment-by-week interaction.

BRIEF-A will be summarized descriptively over time utilizing observed and change from Baseline scores. Treatments will be compared at each time point utilizing MMRM models on change from Baseline scores. The model will include fixed effects for treatment, week, baseline value, and the treatment-by-week interaction.

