7.5 Other Efficacy Analyses

Similar to the BRIEF-A, DERS and ASQ scale scores will be summarized descriptively over time utilizing observed and change from Baseline scores. Treatments will be compared at each time point utilizing MMRM models on change from Baseline scores. The model will include fixed effects for treatment, week, baseline value, and the treatment-by-week interaction.

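### The SAP subtracts the 11 reversed DERS items without adding a constant back, which shifts observed DERS scores down by up to 66 points; separately, the CGI models leave out the baseline CGI-S rated at Visit 2 (minor)

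*SAP*

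**What the plan says.** **DERS.** SAP 7.2.6 describes the scale as "consisting of 36 items scored on a range of 1 (almost never) to 5 (almost always". It lists six subscales, flags reversed items with an R, and takes the total as the sum of the subscales. One subscale is made up entirely of reversed items: "DERS Awareness subscale score (sum of items 2R, 6R, 8R, 10R, 17R, 34R". The note under the key says that R marks a "reverse-scored item which is calculated by subtracting the item score rather than adding". SAP 7.5 then plans both levels and changes: "Similar to the BRIEF-A, DERS and ASQ scale scores will be summarized descriptively over time utilizing observed and change from Baseline scores". Its model is fitted to change, with the baseline value as a covariate. Protocol 6.3.6 gives a different length: "The DERS is a validated non-disease state scale consisting of 39 items".

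**CGI.** For CGI-S and CGI-I treated as continuous, Protocol 9.5 states: "The model will include fixed effects for treatment, week, and the treatment-by-week interaction". SAP 7.4.2 lists the same three terms. The AISRS model (SAP 7.4.1), the BRIEF-A model (SAP 7.4.2) and the DERS and ASQ models (SAP 7.5) each include the baseline value. CGI-S is rated at Visits 1 through 7 (SAP 7.2.2), and a Visit 2 score of 4 or greater is an entry criterion (Protocol 4.1).

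**The concern.** Reversing an item on a 1-to-5 scale means reflecting it within 1 to 5. Subtracting it also changes the direction, but moves its contribution to between -5 and -1. A programmer who follows the SAP literally will produce DERS levels that are not on the DERS scale. The size of the shift differs by subscale, from 0 to 36 points, so the observed subscale levels could not be read side by side. Protocol 3.2.3 wants to know which facets of emotional dysregulation change, so the subscale tables will be read.

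For the CGI, a covariate that should exist for every eligible randomized subject goes unused. Randomization is not stratified by site and no other stratification factor is named (Protocol 5.4, SAP 2.5), so nothing else in the CGI model handles a chance imbalance in starting severity. The outcome is worded as Visit 7 compared with Baseline, but the SAP does not say whether the modelled CGI-S response is the score or the change. The BRIEF-A paragraph that follows does say.

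**Working it through.** **1. The key.** Counting the items in SAP 7.2.6 gives 6 + 5 + 6 + 6 + 8 + 5 = 36. Each of items 1 to 36 appears once, so the SAP's own count is reproduced. Eleven carry R (1, 2, 6, 7, 8, 10, 17, 20, 22, 24, 34), leaving 25 forward items.

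**2. Ranges.** With F forward and R reversed items scored 1 to 5:
- as written, minimum = F - 5R and maximum = 5F - R;
- on scale (6 minus the item), minimum = F + R and maximum = 5(F + R);
- each reversed item contributes -x instead of 6 - x, so the shift is 6R.

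| Score | F | R | As written | On scale | Too low by |
|---|---|---|---|---|---|
| Non-acceptance | 6 | 0 | 6 to 30 | 6 to 30 | 0 |
| Goals | 4 | 1 | -1 to 19 | 5 to 25 | 6 |
| Impulse | 5 | 1 | 0 to 24 | 6 to 30 | 6 |
| Awareness | 0 | 6 | -30 to -6 | 6 to 30 | 36 |
| Strategies | 7 | 1 | 2 to 34 | 8 to 40 | 6 |
| Clarity | 3 | 2 | -7 to 13 | 5 to 25 | 12 |
| Total | 25 | 11 | -30 to 114 | 36 to 180 | 66 |

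For the total: 25 - 55 = -30; 125 - 11 = 114; 6 x 11 = 66. A true total of 116 would be reported as 50, which is on the scale and raises no alarm.

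**3. Effect on the comparisons.** Let S be the on-scale score and W = S - 6R the score as written. With complete items, W at Visit 7 minus W at Visit 2 equals S at Visit 7 minus S at Visit 2, because the constant cancels. Shifting the baseline covariate by a constant alters only the intercept. Simulated item responses for 312 subjects confirmed this: the largest difference in change score was 0, and treatment estimates, standard errors and p-values agreed under both scorings.

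**4. CGI precision.** Let rho be the within-arm correlation between Visit 2 and Visit 7 CGI-S, and k the Visit 2 SD divided by the Visit 7 SD. Neither is in the documents; both are assumed. These formulas treat Visit 7 alone, as an approximation to the repeated-measures model.
- Response is the score: variance with baseline / without = 1 - rho². For rho 0.2 to 0.6 this is 0.96 to 0.64, a cut of 4% to 36% (standard error 2% to 20% smaller).
- Response is the change: the ratio is (1 - rho²) / (1 + k² - 2·rho·k). Over the same rho, the cut is 0% to 9% at k = 0.5, 2% to 21% at k = 0.7, and 20% to 40% at k = 1. For example, at k = 0.5 and rho = 0.5, 0.75 / 0.75 = 1, so there is no gain.

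The entry rule confines baseline CGI-S to 4 through 7 on a 7-point scale. That narrows its spread and points to the lower end of these ranges.

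**The case against.** The strongest reply on the DERS is that a programmer who knows the scale would reflect the items anyway, and that the DERS is exploratory with comparisons made on change. The second half stands. The first does not remove the fault: the SAP is the specification, and it sets subtraction against adding with no constant.

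Three stronger readings are tempting, and the documents do not support them.
- A reader might infer that all observed DERS values would be impossible. That is certain only for Awareness. The as-written and on-scale ranges overlap for the total (36 to 114), Strategies (8 to 34), Impulse (6 to 24), Goals (5 to 19) and Clarity (5 to 13), and Non-acceptance is correct.
- A reader might infer that subtraction also corrupts change scores when items are blank, since the missing-data scenarios in SAP 7.1.1 are only "1) missing or invalid data for individual questions in the AISRS; and (2) missing AISRS total scores at individual visits". But suppose sums use available items, which the SAP does not state, and a reversed item is answered x at one visit only, with true answer y at the other. The change is then wrong by y points under subtraction and by 6 - y under reflection. Both errors are 1 to 5 points. Over all 50 combinations of answers and blank visit, each method is closer in 20 and they tie in 10. Reflection does not cure this; it is a separate question about a missing-item rule.
- A reader might infer that 36 versus 39 items is a live contradiction. It may only be a version difference. The SAP is based on protocol Version 3.0 (SAP 12.1), while the supplied protocol logs only Amendment #1. The SAP also has a cannabis screen (8.5) and an HCV RNA row in its schedule (14.1) that Protocol 6.4.6 and Table 6.1.1 lack.

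On the CGI, the other side can say that SAP and protocol agree, so the model is a consistent pre-specified choice; that CGI-I is already rated relative to Baseline; and that a Cochran-Mantel-Haenszel test is planned as well. All true. The omission is a forgone improvement, not a contradiction.

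**Conclusion.** Both parts hold, at minor severity.

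The DERS rule is wrong as written. Observed scores are too low by 66 on the total, 36 on Awareness, 12 on Clarity and 6 each on Goals, Impulse and Strategies. This rests only on the SAP's own key and item range. The harm is confined to the observed-score summaries; with complete items, no change score, contrast or p-value moves.

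The CGI model is valid without baseline. A reader might infer bias, but randomization keeps the unadjusted contrast unbiased in expectation. What is lost is precision and protection from chance imbalance. The amount depends on a correlation and an SD ratio that the documents do not give, and is probably modest. CGI endpoints are secondary and the DERS is exploratory, so the primary AISRS conclusion and the sample size are untouched.

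**What to change.** 1. In SAP 7.2.6, replace the note so that each reversed item is scored as 6 minus the item score. Confirm that the current protocol version agrees with 36 items, and correct it if it still says 39.
2. In SAP 7.4.2, add baseline (Visit 2) CGI-S as a fixed effect in both the CGI-S and the CGI-I mixed models, and state whether the CGI-S response is the score or the change from Baseline. Because SAP 12.2 declares no changes from the protocol's analyses, record the added covariate there. Leave the Cochran-Mantel-Haenszel test as planned.

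The cost is a few sentences of SAP text and about a line of code for each part, on data already collected. Visits, sample size and the primary analysis do not change. Both edits should be made before unblinding.

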7.2.7 Affective Style Questionnaire (ASQ)

The ASQ is a 20-item questionnaire used to measure individual styles in emotional regulation scored on a range of 1 (not true of me at all) to 5 (extremely true of me). The styles assessed in this instrument are: a) suppression and other strategies to conceal or avoid emotion; b) more able to access emotional information in adaptive problem solving (i.e., to be better able to modulate emotional experience and expression according to contextual demands); and c) reflecting comfort and non-defensiveness in response to arousing emotional responses, thus tolerating the aroused emotional response. The ASQ will be completed at Baseline (Visit 2) and Visit 7.

The following ASQ scores will be assessed:

- ASQ Concealing subscale score (sum of items 1, 5, 9, 10, 13, 15, 18, 20)
- ASQ Adjusting subscale score (sum of items 2, 4, 7, 8, 12, 16, 19)

- ASQ Tolerating subscale score (sum of items 3, 6, 11, 14, 17)
- ASQ Total score (sum of all items)

7.3 Efficacy Outcomes

7.3.1 Primary Efficacy Outcome – AISRS total score

The primary efficacy analysis will be performed on the FAS population. The primary efficacy outcome is the change in AISRS total score from Visit 2 (Baseline) to Visit 7 (End of Study) in AR19 treated subjects compared to placebo.

7.3.2 Secondary Efficacy Outcomes

The primary analysis will be repeated on the PP population using the MMRM analysis described in Section 7.4.1.

The secondary efficacy outcomes include:

- CGI-S at Visit 7 compared to Baseline
- CGI-I at Visit 7
- Changes from Baseline of AISRS subscale scores compared to Visit 7
- Changes from Baseline of the BRIEF-A, subscales, indices, and composites compared to Visit 7

7.3.3 Additional Efficacy Outcomes

Items pertaining to emotional dysregulation are contained in certain domains of several existing tools, including the BRIEF-A, DERS, and ASQ, which will be used in this study.

7.4 Analysis Methods

7.4.1 Primary Efficacy Analyses – AISRS Total Scores

The primary efficacy analysis will be performed on the FAS population. The primary efficacy outcome is the change from baseline in AISRS total score at Visit 7 (Week 5) in AR19 (20 and 40 mg/day) versus placebo. To account for these comparisons, a Bonferroni multiple comparison adjustment will be utilized. Both comparisons will be conducted at the 0.025 (0.05/2) alpha level. No other adjustments for multiplicity will be applied to any other endpoints or comparisons. Change from Baseline in AISRS at Visit 7 will be compared between each of the two different AR19 dose groups and the placebo group.

The key elements of the primary efficacy analysis are as follows:

Data: AISRS total scores measured at Baseline through Visit 7. All available data will be used; there will be no imputation of missing data.

Model: Restricted maximum likelihood (REML)-based MMRM analysis

Fixed effects: The following fixed effects are planned:

- Treatment (class effect: AR19 20 mg/day, AR19 40 mg/day, placebo)
- Week (class effect: Weeks 1, 2, 3, 4, 5)
- Baseline AISRS total score
- Treatment-by-week interaction

Residual Variance-Covariance Matrix: An unstructured correlation matrix will be used to model the within-patient errors and restricted maximum likelihood estimation will be used. The Kenward-Roger method will be used for the denominator degrees of freedom. Should the model fail to converge with an unstructured covariance matrix, alternative covariance structures will be applied, in the following order, until the model converges: heterogeneous Toeplitz, heterogeneous compound symmetry, then heterogeneous autoregressive(1).

The null hypothesis:

H_0 : Change from baseline AISRS total scores at Visit 7 are the same for AR19 and placebo

will be tested against the two-sided alternative hypothesis

H_1 : Change from baseline AISRS totals scores at Visit 7 are not the same for AR19 and placebo.

Within this model, pairwise comparisons (using least squares [LS] mean contrasts) will be made to compare AISRS at Visit 7 for each AR19 dose level with placebo separately (primary efficacy outcome). Treatments will also be compared at other weeks as secondary analyses. If differences between baseline characteristics exist between the three treatment groups in this comparison, it will be investigated whether adjustment for these characteristics is clinically relevant and necessary as a sensitivity analysis.

The estimand of this primary efficacy analysis is the mean treatment difference, AR19 (20 mg/day and 40 mg/day) vs. placebo, of change from baseline in AISRS total scores among all randomized subjects who remain in the study for the duration of the blind treatment period, regardless of treatment adherence.

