Statistical Methods	
Sample Size: Approximately 87 patients per treatment group will provide approximately 90% power to detect a 7.0-point difference in mean change from Baseline to Visit 7 in the AISRS total score between one of the AR19 doses and placebo with a standard deviation of 13.0 and Type I error of 0.025 using a two-sample t test. To account for an approximate 20% dropout rate, a total of 104 subjects will be randomized to each of the three treatment groups for a total of 312 randomized subjects.
 
Statistical Methods: All continuous study assessments will be summarized by treatment and time point using descriptive statistics (n, mean, median, standard deviation, minimum, and maximum). All categorical study assessments will be summarized by treatment and time point using frequency counts and percentages. Hypothesis testing, unless otherwise indicated, will be two-sided and performed at the 5% significance level. Full details will be included in a statistical analysis plan (SAP).
 
The primary efficacy endpoint is change from Baseline in AISRS total score at Visit 7. A Bonferroni adjustment will be utilized for the primary efficacy analysis where each AR19 dose will be tested against placebo separately using an alpha

----------------------------	--

of 0.025 for each test. No other adjustments for multiplicity will be applied to any other endpoints or comparisons.

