## **9 STATISTICAL ANALYSES**

### **9.1 Determination of Sample Size**

The primary efficacy endpoint is change from Baseline in AISRS total score at Visit 7 (Week 5). A Bonferroni adjustment will be utilized for the primary efficacy analysis where each AR19 dose will be tested against placebo separately using an alpha of 0.025 for each test.

Eighty-seven (87) subjects per treatment group will provide approximately 90% power to detect a 7.0-point difference in mean change from Baseline to Visit 7 in the AISRS total score between one of the AR19 doses and placebo with a standard deviation of 13.0 and Type I error of 0.025 using a two-sample test. To account for an approximate 20% dropout rate, a total of 104 subjects will be randomized to each of the three treatment groups for a total of 312 randomized subjects.

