2. PROTOCOL SUMMARY

2.1 Introduction

Attention deficit hyperactivity disorder (ADHD) is a neurobehavioral disorder which typically presents in childhood. As defined in the Diagnostic and Statistical Manual of Mental Disorders, Fifth Edition (DSM-5™), ADHD is characterized by pervasive and impairing symptoms of inattention, hyperactivity, and impulsivity which begin in childhood. ADHD often persists into adulthood with one-half to two-thirds of child patients continuing to be symptomatic adults. The estimated prevalence of ADHD in adults in the United States is 4.4%. ADHD causes significant impairment in patients throughout the lifespan. Adults with ADHD are more likely to quit a job or be fired, have auto accidents, experience sudden changes in personal or career goals, and have higher perceived social and emotional stress.

Specific etiology of this disorder is unknown, and there is no single diagnostic test. It is apparent that the prefrontal cortex (PFC) plays a significant role in maintaining executive function, and that patients with ADHD appear to have less-than-adequate PFC activity, resulting in an overall inability to regulate impulsive behavior. Adequate diagnosis requires the use not only of medical but also of special psychological, educational, and social resources. Learning may or may not be impaired. The diagnosis must be based upon a complete history and evaluation of the patient and not solely on the presence of the required number of DSM-5™ characteristics.

The core symptoms used to diagnose ADHD in adults are inattention and hyperactivity-impulsivity. It has, however, been recognized for decades that many adult ADHD patients experience clinically significant levels of emotional dysregulation. Items pertaining to emotional dysregulation are contained in certain domains of several existing tools, including the Behavior Rating Inventory of Executive Function—Adult Version (BRIEF-A), Difficulties in Emotion Regulation Scale (DERS), and Affective Style Questionnaire (ASQ).

Controlled clinical trials have consistently demonstrated that stimulants (amphetamine and methylphenidate) substantially reduce the characteristic symptoms and functional impairment of patients with ADHD. Stimulants have a large effect size, with a mean of 0.73 to 0.96 in placebo-controlled adult ADHD trials.

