2.7 Sample Size Determination

The primary efficacy endpoint is change from Baseline in AISRS total score at Visit 7 (Week 5). A Bonferroni adjustment will be utilized for the primary efficacy analysis where each AR19 dose will be tested against placebo separately using an alpha of 0.025 for each test.

Eighty-seven (87) subjects per treatment group will provide approximately 90% power to detect a 7.0-point difference in mean change from Baseline to Visit 7 in the AISRS total score between one of the AR19 doses and placebo with a standard deviation of 13.0 and Type I error of 0.025 using a two-sample test. To account for an approximate 20% dropout rate, a total of 104 subjects will be randomized to each of the three treatment groups for a total of 312 randomized subjects.

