The goal of the tipping point analysis is to determine how robust the results of the primary analysis are to varying its assumption that the change from baseline at Visit 7 AISRS total scores for subjects that discontinue early from the AR19 group is the same as the completers in the AR19 group. In particular, this analysis examines how altering this assumption to allow the discontinued subjects to have better and worse outcomes will impact the resulting estimates of the treatment effect. This will quantify the range of values which the assumptions can take on and still provide the same conclusions as the primary analysis, giving a very direct measure of the sensitivity of the primary analysis to deviations from the assumptions using an approach that has missing values for AR19 discontinuation subjects imputed. Missing AISRS total score data in the AR19 group will be imputed based on observed values in the AR19 group and likewise, missing AISRS total score values in the placebo group will be imputed based on observed values in the placebo group.

In this analysis, the estimate of the effect in the AR19 subjects may be viewed as a weighted average of the observed average for AR19 completers and the average MAR estimate for AR19 subjects. Shift values of .05 (treated subjects have 5% of the change from baseline AISRS total score as assumed in the primary methodology) through 1 (treated subjects have 100% of the change from baseline AISRS total score as assumed via the primary methodology) will be applied at increments of .05 and reported. The primary analysis will be rerun for all shift values and the resulting treatment difference, 97.5% CI and p-value for each shift value will be reported; the wider the range of values that result in no change in interpretation, the more robust the analysis results may be considered to be.

Subjects receiving placebo who discontinue prior to the end of the treatment period will have their change from baseline AISRS total score value imputed

based on the assumption that they respond to treatment in a similar manner to the placebo subjects who completed the study. For subjects receiving AR19 who discontinue prior to the end of the treatment period, the assumed response to treatment will be examined in increments from worst (subjects respond in a similar manner to the placebo subjects who completed the study) to best (subjects respond in a similar manner to the AR19 subjects who completed the study).

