The steps to implement the tipping point analysis are as follows:

- 1) A mixed model repeated measures (MMRM) model will be run using all observed data and the LS mean in the AR19 group (20 and 40 mg/day separately) of change from baseline at Week 7 in AISRS total score will be calculated.
- 2) Missing data will be imputed based on the MAR assumption using multiple imputation procedure (PROC MI) to create 100 complete datasets with 20 burn-in iterations.
- 3) For subjects in the AR19 dose groups, the imputed values from Step 2 will be “penalized” by adding a percentage (i.e. 5%, 10%, 15%, 20%, etc. of the LS mean treatment difference) of the absolute value of the mean change calculated from Step 1; for the placebo group, no “penalty” will be taken for the imputed values.
- 4) Each newly generated complete dataset from Step 3 will be analyzed using the primary analysis MMRM model and results from all 100 datasets will be combined (PROC MIANALYZE) to generate inferences.
- 5) This analysis (Steps 3-4) will be repeated for a range of values (i.e. 5%, 10%, 15%, 20%, etc. of the treatment difference) until either the tipping point (where statistical significance of the treatment effect is lost) is identified or the 100% penalty is applied.

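### Optional improvement: Holm instead of a fixed 0.025 per dose keeps the 5% family-wise limit, loses no rejection, and can raise both-dose power (about 83.6% to 89.7% if both doses have the planned effect)

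*SAP*

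**What the plan says.** The primary analysis makes two contrasts at Visit 7, 20 mg and 40 mg each against placebo. The level is fixed in advance. SAP 7.4.1 and Protocol 9.4 say "Both comparisons will be conducted at the 0.025 (0.05/2) alpha level", and the protocol synopsis says "each AR19 dose will be tested against placebo separately using an alpha" of 0.025. Protocol 9.1 and SAP 2.7 repeat this. There is no step-down rule.

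The sample size is justified for a single comparison. Protocol 9.1 states "Eighty-seven (87) subjects per treatment group will provide approximately 90% power to detect a 7.0-point difference in mean change", and SAP 2.7 describes that difference as one "between one of the AR19 doses and placebo with a standard deviation of 13.0". Neither document sets a power target for showing both doses.

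Two other parts of the SAP depend on the level:
- SAP 3 sets 97.5% as the confidence level for intervals.
- In the tipping-point analysis (SAP 7.1.1.2), "the resulting treatment difference, 97.5% CI and p-value for each shift value will be reported". Step 3 shifts both doses ("For subjects in the AR19 dose groups, the imputed values from Step 2 will be" penalised), and step 5 continues until "the tipping point (where statistical significance of the treatment effect is lost) is identified" or the penalty reaches 100%.

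**The concern.** Under single-step Bonferroni the second dose is judged at 0.025 even when the first has already succeeded. At that point only one hypothesis remains, and it could be tested at 0.05 without exceeding the 5% family-wise limit. The plan adjusts no other endpoint for multiplicity, so the unused level serves no other purpose.

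Protocol 1.3 expects both doses to show efficacy, so the second dose matters. What is at stake is a trial that ends with one dose significant and the other with a p-value between 0.025 and 0.05. The present rule counts that second dose as a failure, and Holm would count it as a success.

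**Working it through.** **Inputs.** 87 per arm, difference 7.0, SD 13.0, two-sided 0.025 per dose (Protocol 9.1, SAP 2.7); 1:1:1 allocation with a shared placebo arm (SAP 2.5); 104 randomised per arm with 20% dropout, 104 × 0.8 = 83.2 (SAP 2.7); cited stimulant effect sizes 0.73 to 0.96 (SAP 2.1).

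**1. The plan's own figure.** The standardised effect is 7/13 = 0.538 and the noncentrality is 0.538 × √(87/2) = 3.551. The normal approximation gives Φ(3.551 − 2.241) = Φ(1.310) = 90.5%. The noncentral t with 172 df gives 90.0%. The stated 90% is reproduced.

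**2. Error control under Holm.** The smaller p-value is tested at 0.025 and, only if that is significant, the larger at 0.05.
- Both nulls true: a false rejection needs the smaller p ≤ 0.025, which has probability at most 2 × 0.025 = 0.05.
- One null true: a false rejection needs that dose's p ≤ 0.05, which has probability at most 0.05.

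Holm rejects whenever Bonferroni does.

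**3. Both-dose power, normal approximation.** With equal true effects, the two statistics have correlation 0.5. Write P(a, b) for the probability that the first statistic exceeds a and the second exceeds b, with c1 = 2.241 and c2 = 1.960.
- Bonferroni, both doses: P(c1, c1) = 0.840.
- Holm, both doses: 2 P(c1, c2) − P(c1, c1) = 2 × 0.8696 − 0.8400 = 0.899.
- At least one dose, under either rule: 2 × 0.9049 − 0.8400 = 0.970.

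**4. t-type model.** Each statistic uses the SD pooled over three arms, df = 3(87 − 1) = 258, by numerical integration checked by simulation. Effect size 0.73 corresponds to 0.73 × 13 = 9.49 points.

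| Both doses equal | Both-dose power, Bonferroni | Holm | Gain (points) |
|---|---|---|---|
| 7 points, SD 13, n = 87 | 83.57% | 89.65% | 6.1 |
| 7 points, SD 13, n = 83 | 81.26% | 87.94% | 6.7 |
| 7 points, SD 12, n = 87 | 90.21% | 94.30% | 4.1 |
| 7 points, SD 11, n = 87 | 95.21% | 97.47% | 2.3 |
| 8 points, SD 13, n = 87 | 93.56% | 96.47% | 2.9 |
| 9.49 points, SD 13, n = 87 | 98.98% | 99.55% | 0.6 |

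In the first row, at least one dose succeeds in 96.82% of trials under both rules. Exactly one succeeds under Bonferroni in 96.82 − 83.57 = 13.25%, and Holm turns 89.65 − 83.57 = 6.08 points of these into success for both.

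**5. A weaker 20 mg dose** (assumed values; n = 87, SD 13). The power shown is for 20 mg.

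| 20 mg effect | 40 mg effect | Bonferroni | Holm | Gain (points) |
|---|---|---|---|---|
| 6 | 7 | 78.46% | 84.58% | 6.1 |
| 5 | 7 | 61.14% | 70.38% | 9.2 |
| 6 | 9.49 | 78.46% | 85.77% | 7.3 |
| 5 | 9.49 | 61.14% | 71.44% | 10.3 |

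**6. False positives.** With both nulls true, any rejection occurs in 4.64% under either rule. With one dose null, its rejection rate rises from 2.50% to 4.52% if the other dose has 7 points, and to 4.95% if it has 9.49.

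**The case against.** The plan promises power for one dose, and Bonferroni delivers it. On the outcome closest to the stated objective, that AR19 differs from placebo, Holm adds nothing: the chance of at least one success is 96.8% either way. This stands, and it makes the change optional.

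The gain may also be small. SAP 2.1 says "Stimulants have a large effect size, with a mean of 0.73 to 0.96 in placebo-controlled adult ADHD trials"; if both doses reach even the lower end, the gain is 0.6 points. The planned MMRM adjusts for baseline, which may lower the residual SD, and the SD 11 and 12 rows show the gain shrinking. This stands too. The rows with a weaker 20 mg dose use assumed values, since the documents give no separate effect for that dose.

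Bonferroni at 0.025 also pairs exactly with the 97.5% intervals. Under Holm, a dose gained at the second step has a 97.5% interval that includes zero, and an added 95% interval has no simultaneous coverage. A sponsor may reasonably prefer tests and intervals that always agree. That is a cost in presentation, because Holm never loses a rejection and the family-wise limit is unchanged.

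A reader might infer that the trial is underpowered or its multiplicity control faulty because both-dose power is 83.6%. The documents do not support this: they set no both-dose target, the 0.025 level is stated consistently, and it controls the error as intended.

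**Conclusion.** Single-step Bonferroni is correct as planned. Holm is a cheap improvement that helps only the second dose. The gain is 6.1 points in both-dose power if both doses truly have 7 points with SD 13 and 87 evaluable per arm. It is 2 to 4 points if the SD is 11 to 12, and 0.6 points if both doses reach effect size 0.73. If 20 mg gives only 5 to 6 points, its own power gains 6 to 10 points.

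That Holm rejects at least as much under the same 5% limit needs no assumption beyond those Bonferroni already makes. Only the size of the gain depends on the true effects and the SD. The figures come from a t-type model at Visit 7, not from the planned MMRM. It would be wrong to read 6.1 points as the expected gain, or as a higher chance that the trial succeeds on at least one dose.

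**What to change.** Make the change before the SAP is signed and the data are unblinded.

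**SAP 7.4.1, Protocol 9.4 and synopsis:**

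> The two AR19-versus-placebo contrasts at Visit 7 will be tested by the Holm procedure at an overall two-sided level of 0.05: the smaller p-value at 0.025 and, only if it is significant, the larger at 0.05. Two-sided 97.5% confidence intervals will be reported for both doses. A dose significant only at the second step will also have a 95% confidence interval, labelled unadjusted.

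**Protocol 9.1 and SAP 2.7:** keep 0.025, stated as the basis of the sample size only.

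**SAP 7.3.2 (per-protocol repeat) and 7.1.1.2 (placebo-based imputation and tipping point):** apply the full Holm procedure to both doses in each. Otherwise the 2.5% default in SAP 3 could be used to judge a dose that won at 0.05.

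**Tipping point.** SAP 7.1.1.2 uses two opposite scales. In the narrative, shift values run from .05 (5% of the assumed change kept) to 1 (all of it kept); in steps 3 and 5, a penalty rises from 5% to 100%. Reconcile them, and use the penalty scale, as a percentage of the LS mean treatment difference:

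> At each penalty, Holm is re-applied to both doses. A dose's tipping point is the smallest penalty at which Holm no longer rejects its null hypothesis.

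**SAP 12.2:** list the change.

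**Cost.** No subjects, visits or data are added. The protocol edits need an amendment, sent to the IRB before implementation (Protocol 10.1). Check them first against protocol Version 3.0, on which SAP 12.1 and 12.2 say the SAP is based. The sponsor also accepts the interval mismatch, a false-positive rate for a null dose of about 4.5% to 4.95% instead of 2.5% when the other dose works, and a tipping point for one dose that depends on the other. If the sponsor prefers exact agreement of tests and intervals, one sentence saying so is enough.

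The differing default levels in SAP 3 (2.5%) and Protocol 9.2 (5%) are a separate matter.
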